### **Predicted relationship between timing, price, and response magnitude.**

EO relative to AO.

We predict that the mean magnitude of peak responding for participants assigned to cheap conditions will be higher than those assigned to expensive conditions, holding timing constant. Additionally, we predict the mean magnitude of peak responding will be higher for those participants assigned to EO as compared to AO, holding price constant. Further, we predict a timing by price interaction such that the difference in mean peak responding in cheap and expensive conditions will be bigger in

**Power Analysis.** Power analysis and sample size calculations were conducted using G\*power software. Since our study represents a novel contribution to the field, we cannot rely on previous literature to estimate the population value of R-squared or the appropriate effect size. However, our pilot data suggest the effect size will not be small. Thus, we calculated sample size based on a benchmark value for Cohen's  $f^2$  of 0.15 that corresponds to a medium effect size for R-squared (Cohen, 1988). To achieve 80% power in a regression model with three predictors and  $\alpha = .05$ , the number of required participants is 77. With a sample of 77, the power to find any one of the three predicted effects (given medium effect size) is 88. Since participants will be equally distributed across four groups, we budgeted time/effort for 80 participants. Under our most conservative study assumptions, AIMS 1 & 2 are adequately powered.

### **6.0 Reporting of Adverse Events or Unanticipated Problems involving Risk to Participants or Others**

This is a low-risk study. The PI ([name]) will review all data on a weekly basis and all adverse events (AE) will be logged on an AE form and will immediately be reported to the IRB.

### **7.0 Study Withdrawal/Discontinuation**

Prior to each appointment, we will re-assess assent to participate by asking clients if they would like to work with us. When/if assent is not given, we will not conduct appointments. We will individualize appointment parameters (i.e., appointment duration, responses targeted, reinforcers delivered) based on ongoing assessments of participant preferences (see study procedures). We will also provide periodic reminders of how participants can terminate sessions and/or appointments (by simply saying that they would like to stop). If participants indicate they no longer wish to participate in the study, we will promptly terminate their participation with no consequence to them (i.e., participants will be paid for all time spent in research activities, RAs will not try to convince participants to stay in the study, and RAs will continue to interact with participants in pleasant and respectful ways).

### **8.0 Statistical Considerations**

**Power Analysis.** Power analysis and sample size calculations were conducted using G\*power software. Since our study represents a novel contribution, we cannot rely on previous literature to estimate the population value of R-squared or the appropriate effect size. However, our pilot suggests the effect size will not be small. Thus, we calculated sample size based on a benchmark value for Cohen's  $f^2$  of 0.15 that corresponds to a medium effect size for R-squared (Cohen, 1988). To achieve 80% power in a regression model with three predictors and  $\alpha = .05$ , 77 participants are required. With this sample, the power to find any one of the three predicted effects (given medium effect size) is 88%. As participants will be equally distributed across four groups, we budgeted effort for 80 participants. Under our most conservative study assumptions, AIMS 1 & 2 are adequately powered.

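### The 80% power at 77 participants belongs to the 3-df whole-model test; the 88% given for the individual Aim 2 effects does not follow from the stated inputs, and power for the interaction is not shown

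*Combined protocol and SAP*

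**What the plan says.** The power paragraph appears twice: at the end of section 5.0 (Power Analysis, after the predicted relationships) and in section 8.0. Both adopt Cohen's f² of 0.15, a value "that corresponds to a medium effect size for R-squared". The sample size follows: "To achieve 80% power in a regression model with three predictors and" alpha = .05, 77 participants are needed. Section 8.0 continues that "the power to find any one of the three predicted effects (given medium effect size) is 88" per cent, and section 5.0 has the same sentence: "With a sample of 77, the power to find any one of the three predicted effects (given medium effect size) is 88". Because four equal groups are planned, 80 participants are budgeted. Both paragraphs close with "Under our most conservative study assumptions, AIMS 1 & 2 are adequately powered".

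The Data Analysis Plan in section 5.0 sets three questions for the Aim 2 regression: the effect of timing, the effect of relative price, and whether the two interact. Price and timing enter as dummy-coded predictors. All three effects are predicted to be present. Peak responding in the cheap conditions "will be higher than those assigned to expensive conditions, holding timing constant"; "we predict the mean magnitude of peak responding will be higher for those participants assigned to EO as compared to AO, holding price constant"; and "we predict a timing by price interaction such that the difference in mean peak responding in cheap and expensive conditions will be bigger in" EO than in AO. Section 2.0 (H2) is more open: price only, timing only, or an interaction.

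**The concern.** A regression with three predictors offers two kinds of test. The whole-model F test asks whether any of the three terms matters (3 df). The coefficient tests ask about one term each (1 df). Aim 2 needs the second kind, and the sample size looks like the first.

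The plan does give a figure for the individual effects, 88%, but does not say what effect size each effect is assumed to have. The phrase about a medium effect next to any one effect suggests f² = 0.15 for that effect. The link to R-squared suggests 0.15 for all three together. The two readings give very different power.

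The interaction has most at stake. It is the term that separates the third H2 pattern from the first two, and a reader needs its power to judge what a non-significant result means.

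**Working it through.** **Inputs.** From sections 5.0 and 8.0: alpha .05; f² = 0.15; three predictors; N = 77 required and 80 planned; four equal groups. Assumed, because not stated: two-sided tests, no multiplicity adjustment, and the usual fixed-model regression convention.

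**Formula.** Power = P(F′(u, v, λ) > F₀.₉₅(u, v)), where u is the numerator df, v = N − 4 and λ = f² × N.

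**Step 1: reproduce the 80%.** With u = 3, N = 77: v = 73, λ = 0.15 × 77 = 11.55, critical F = 2.730, power 80.2%. At N = 76 it is 79.6%. So 77 is exactly the smallest N for the 3-df whole-model test. At N = 80 this test has 81.9%.

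**Step 2: try to reproduce the 88%.** With u = 1, N = 77, partial f² = 0.15: λ = 11.55 again, critical F = 3.972, power 91.8%. This is 3.8 points above the stated figure. A 1-df power of 88% at N = 77 needs partial f² = 0.131.

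One possible origin is a mix-up of scales. An f² of 0.15 corresponds to R² = 0.15 / 1.15 = 0.1304. Entered as if it were f², this gives λ = 0.1304 × 77 = 10.04 and power 87.8%. Other routes also come near 88%: the 3-df test at alpha .10 gives 88.1%, and the chance that at least one of three tests is significant, with f² = 0.05 each, is 86.2% by simulation. The documents do not settle which, if any, was used.

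**Step 3: read 0.15 as the whole-model value.** In a balanced 2×2 with orthogonal (-1/+1) coding, the three partial f² values add up to the model f². The plan gives no split, so the shares below are assumptions (1-df test, N = 80, v = 76).

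| Share of 0.15 | Partial f² | λ = f² × 80 | Power |
|---|---|---|---|
| one third | 0.05 | 4.0 | 51% |
| one half | 0.075 | 6.0 | 68% |
| about two thirds | 0.101 | 8.1 | 80% |
| all | 0.15 | 12.0 | 93% |

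At N = 77 the one-third share gives λ = 3.85 and power 49.1%. The 80% threshold at N = 80 is partial f² = 0.1007, and 0.1007 / 0.15 = 0.67. For a smaller effect, partial f² = 0.02 (λ = 1.6), power is 24%.

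**Step 4: where the two readings agree.** If only one effect is non-null, as in the price-only or timing-only pattern of H2, that effect carries the whole 0.15. Its main-effect test then has 91.8% at 77 and 92.8% at 80. The readings part when several effects are present together, as section 5.0 predicts.

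**Step 5: coding.** With 0/1 dummy variables and a product term, the price coefficient is the price effect at the reference level of timing, and likewise for timing. These are simple effects, and the additive split in step 3 does not apply to them. With three equal -1/+1 coefficients, for example, the simple effect at the level coded -1 is zero, and the 0/1 tests of price and timing then reject only about 5% of the time. The interaction test is the same under either coding.

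**Sensitivity to blocking.** If the 20 tetrads were added as terms at N = 80, error df would be 80 − 1 − 19 − 3 = 57. With f² unchanged, power is 92.6% at partial f² = 0.15 and 50.3% at 0.05, so the picture is the same.

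**The case against.** The strongest reply is that the 88% was meant for each effect with its own medium f² of 0.15. The wording favours this, and the R²-for-f² slip would reproduce the figure to rounding. On that reading the error is about 4 points in the safe direction, the interaction has 92.8% power at N = 80, and the sample size is unaffected. This stands, and it is why the point concerns what is stated and not the size of the study. It does not close the matter, because the same paragraph defines 0.15 through R-squared and nowhere gives an effect size per term.

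A reader might infer more than the documents support:

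- *That each Aim 2 test has about even odds of success.* The 49% and 51% need a whole-model 0.15 and an equal split, and no section gives a split.
- *That interaction power cannot exceed 51%.* This needs the whole-model reading and also that the predicted price and timing effects hold at each level of the other factor. If they hold only on average, there is no such ceiling.
- *That 0.15 for each effect makes the model f² 0.45, for which 29 participants would do, so that the 77 contradicts itself.* The sum holds only for orthogonal coding. With the planned dummy coding, 0.15 on each coefficient gives a model f² of 1.90 or 0.20, depending on the sign of the interaction.
- *That the plan would treat a non-significant interaction as proof of a price-only or timing-only pattern.* No section says so.

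**Conclusion.** The point holds in limited form. The 80% at 77 is correct for the 3-df whole-model test, which is not one of the three Aim 2 questions. The 88% does not follow from alpha .05, N = 77 and f² = 0.15 for any single 1-df test; the value is 91.8%, so the stated figure is about 4 points low if 0.15 is meant per effect. If 0.15 is the whole-model value, power for each effect depends on an unstated share and, for the shares shown, runs from 51% to 93% at N = 80.

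The closing claim of adequate power under the most conservative assumptions is therefore not shown for the interaction test unless that effect alone has partial f² of about 0.10 or more. This does not show that the study is too small, and it says nothing about Aim 1, whose power was not examined here. The results rest on two-sided alpha .05 without multiplicity adjustment, equal groups, and orthogonal coding for the price and timing effects.

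**What to change.** 1. In both power paragraphs (sections 5.0 and 8.0), replace the sentences with the 80% and the 88% by: *With 80 participants the 3-df test of the whole model has 82% power at model f² = 0.15. Each 1-df test in orthogonal (-1/+1) coding (two-sided alpha .05) has 80% power at partial f² = 0.101, and 93%, 51% and 24% at partial f² of 0.15, 0.05 and 0.02.*
2. State the partial f² assumed for price, for timing and for the interaction.
3. For Aim 2, limit the statement of adequate power to the tests and effect sizes for which a power is given. The Aim 1 statement is outside this point.
4. In the Data Analysis Plan (section 5.0), use -1/+1 coding, or report marginal contrasts from the same model, so that the price and timing estimates are main effects and match the power figures.

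The cost is wording and one coding choice. The stated power for the interaction may become less favourable. N, design and data collection do not change.

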## **9.0 Privacy/Confidentiality Issues**

Participant names will be replaced with pseudonyms on all study-related documents. A single Excel file will link participant names and contact information to pseudonyms. All other research documents will not include participant names and will only include associated pseudonyms.

The above-mentioned Excel file will be stored on a secured and password protected computer, as well as on a server provided by Vanderbilt University and only accessible to research personnel. This file will be destroyed at the study's conclusion, leaving no remaining link between identifying information and participant data.

## **10.0 Follow-up and Record Retention**

We anticipate that this study will require two years to complete. Intend to maintain all de-identified records obtained during the study indefinitely. However, files linking participant names and contact information to pseudonyms will be destroyed (deleted) once the study has been completed.

